### 14.5. Primary Analysis

VAS comfort scores will be analyzed using a multivariate Bayesian model for repeated measures to test for the difference between the Test and Control eye drops. The regression model will include sequence and solution as fixed effects. The correlation between measurements across periods will be modeled using unstructured variance-covariance matrix.

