## **4. STUDY DESIGN AND RATIONALE**

### **4.1. Description of Study Design**

The study design is a randomized, double-masked, bilateral, 2 treatment × 2 period, dispensing, 4-visit study.

After a pre-screening assessment, eligible subjects will be invited to attend an initial visit. At study Visit 1, subjects will be consented and screened for inclusion/exclusion criteria. If a subject is found to meet all eligibility criteria, they will be dispensed with the first artificial tears eye drops based on the randomization scheme; otherwise, the subject will be discontinued from the study. After dispensing of the first eye drop solution; NITBUT, LipiView II® measurement at taken at approximately 5 mins, 30 mins, 1 hour, and 2 hours post drop

Subjects will be dispensed with their randomly assigned eye drops and instructed to use them OU at least 3 times a day over a 7-9 day period. The follow-up evaluation (Visit 2) will occur 7-9 days after the initial visit. At this visit questionnaires, LipiView II®, NITBUT, slit lamp findings will be captured.

After completion of Visit 2, there is a 7-9 day washout period during which subjects may use their habitual products, if any, but they will be advised not use any eye drops on the day of Visit 3

Following the washout period, the subject returns for Visit 3 and is dispensed with the second randomized eye drop with NITBUT, LipiView II® measurements at approximately 5 mins, 30 mins, 1 hour, and 2 hours post drop. Subjects will be dispensed with their second randomly assigned eye drops and instructed to use them OU at least 3 times a day over a 7-9 day period. Visit 4 takes place 7-9 days after visit 3, at which questionnaires, LipiView II®, NITBUT, slit lamp findings, final evaluation will take place.

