### 14.2. Sample Size Justification

The plan is to enroll 60 subjects with a target of 50 subjects to complete the study. This is a pilot study and the sample size was not based on any empirical power calculation. The power analysis for different scenarios of size effects ( $\Delta$ ) and inter-subject correlation ( $\rho$ ), assuming a common VAS comfort score variance of 25, are summarized below:

Table 4: Power Analysis for VAS comfort

$\Delta$	$\rho$	Power (%)
5	.30	21.6
	.50	28.4
	.80	59.2
10	.30	64.9
	.50	79.2
	.80	99.2

The power analysis was conducted the SAS procedure PROC POWER procedure for paired tests.

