#### **The Model:**

Let  $\mathbf{y}_{ijk} = (y_{1ij}, y_{2ij})^T$  denote the comfort scores for the  $i^{\text{th}}$  subject, from  $i^{\text{th}}$  site at 1week follow-up. The likelihood of  $\mathbf{y}_{ij}$  is constructed as follow:

$$\mathbf{y}_{ij} \sim N(\boldsymbol{\mu}, \boldsymbol{\Sigma}),$$

where  $\boldsymbol{\mu} = (\mu_1, \mu_2)^T$  and  $\boldsymbol{\Sigma}$  is a 2x2 variance-covariance matrix. Here  $\mu_i, i = 1, 2$ , are given by:

$$\begin{aligned}\mu_1 &= \mu_0 + \beta_1\text{BASE} + \beta_2\text{sequence} + \beta_3\text{Test}, \\ \mu_2 &= \mu_0 + \beta_1\text{BASE} + \beta_2\text{sequence} - \beta_3\text{Test},\end{aligned}$$

Other baseline characteristics such as age, gender DEQ-5 score will also be included as fixed effects when appropriate.

Non-informative prior distributions will be used for the coefficients in the models as well as for the error terms: Independent vague normal  $N(0,1000)$  priors for the regression

coefficients ( $\mu_0$  and  $\beta$ ) and inverse Wishart  $IW(R,2)$  for  $\Sigma$ .  $R$  is determined by  $S = E[\Sigma] = 4R$  where  $S$  is the sample variance-covariance matrix of the  $y_{ij}$ . The Metropolis sampler algorithm as implemented in the MCMC Procedure (SAS 9.4, SAS Institute, Cary, NC) will be used to estimate the posterior distributions of the unknown parameters. Inferences will be made based on a posterior credible interval for the relevant parameters. Results will be reported as regression coefficient mean estimates with 95% credible intervals.

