#### **Hypothesis Testing:**

The null and alternative hypotheses for superiority is as follows:  $H_0: \beta_3 \leq 0$ ,  $H_a: \beta_3 > 0$ . Superiority will be declared if the lower bound of the 2-sided 95% credible interval of the difference between Test and Control is greater than 0:  $P(\beta_3 > 0|y) \geq 0.95$ .

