#### **14.6. Secondary Analysis**

OSDI scores will be analyzed using the same model described in the primary analysis. The null and alternative hypotheses for superiority is as follows:  $H_0: \beta_3 \geq 0$ ,  $H_a: \beta_3 < 0$ . Superiority will be declared if the upper bound of the 2-sided 95% credible interval of the difference between Test and Control is less than 0:  $P(\beta_3 < 0|y) \geq 0.95$ .

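### The primary crossover model has no period term, and β3 is not tied to the Test minus Control difference it is meant to test and report

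*Combined protocol and SAP*

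**What the plan says.** Section 4.1 describes a "2 treatment × 2 period, dispensing, 4-visit study". Section 14.5 says that "The regression model will include sequence and solution as fixed effects" and that "The correlation between measurements across periods will be modeled using unstructured variance-covariance matrix".

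Under The Model in 14.5, the two comfort scores per subject have means

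- μ1 = μ0 + β1·BASE + β2·sequence + β3·Test
- μ2 = μ0 + β1·BASE + β2·sequence − β3·Test

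Age, gender and DEQ-5 score may be added. The same subsection says "Results will be reported as regression coefficient mean estimates with 95% credible intervals". Hypothesis Testing sets H0: β3 ≤ 0 and declares superiority if the "lower bound of the 2-sided 95% credible interval of the difference between Test and Control is greater than 0". Section 14.6 adds that "OSDI scores will be analyzed using the same model described in the primary analysis".

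**The concern.** **Period is missing from the mean.** Sequence moves both components of a subject by the same amount, so it cannot absorb a shift between periods. The optional covariates are baseline characteristics. BASE carries no period index, although Table 3 schedules a pre-drop VAS at both Visit 1 and Visit 3. Only if BASE were each period's own pre-drop value could it take up part of a drift. The washout in 4.2 is aimed at carry-over, not at period effects.

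**β3 has no fixed meaning.** Test is given no values, and components 1 and 2 are described only as comfort scores at the one-week follow-up. The reference to correlation across periods hints that they are periods but does not say so. Two programmers could follow this text and report VAS and OSDI differences that differ by a factor of two. Under some codings β3 would also carry the period effect.

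**Working it through.** **Inputs.** Section 14.2: 50 completers, Δ of 5 or 10, ρ of 0.30, 0.50 or 0.80, paired test. Section 14.4: 5% error rate. Table 1: 25/25 planned completers. The documents give no period effect; 0, 5 and 10 VAS points are assumptions.

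**Step 1: reproduce Table 4.** SD of the paired difference = SD·√(2(1−ρ)), n = 50, two-sided 5%, noncentral t. With SD = 25 the powers are 21.6, 28.4, 59.2 (Δ 5) and 64.9, 79.2, 99.2% (Δ 10), exactly as printed. SD = 5, the literal reading of a variance of 25, does not reproduce the table, so SD 25 is used below.

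**Step 2: what β3 estimates.** Let τ be Test minus Control and π be period 2 minus period 1. The expected y1 − y2, with components as periods, is τ − π in Test/Control and −τ − π in Control/Test. If Test has the same value in both equations, the plan's model sets this contrast to 2·β3·Test. With τ = 10, 25/25 completers and the model as written:

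| Reading | β3 at π = 0 | β3 at π = 5 |
|---|---|---|
| Periods, Test = ±1 by sequence | 5.0 | 5.0 |
| Periods, Test = ±½ by sequence | 10.0 | 10.0 |
| Components are treatments, Test = 1 | 5.0 | 5.0 |
| Periods, Test = 1 if Test first, else 0 | 5.0 | 2.5 |
| Periods, Test = 1 in the period Test is used, else 0 | 0.0 | −5.0 |

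In the last row the sign flip makes y1 − y2 equal β3 in both sequences, so β3 = −π. That reading is the least coherent, because the sign flip already encodes the switch.

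**Step 3: effect on the report.** At ρ = 0.5 the SE of the difference is 25·√(2·0.5)/√50 = 3.54. A difference of 10 has a 95% interval of about 2.9 to 17.1. Under ±1 coding the reported coefficient is 5.0 (1.4 to 8.6), which resembles the Δ = 5 row of Table 4.

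**Step 4: omitted period, equal sequences, ± coding.** The subject-level difference Test − Control has mean τ − π in one sequence and τ + π in the other. Without a period term the estimated variance is about σd² + π²·50/49, where σd is the SD of the paired difference. At ρ = 0.8, σd² = 625·0.4 = 250:

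- π = 0: √(250/50) = 2.24
- π = 5: √((250 + 25.5)/50) = 2.35
- π = 10: √((250 + 102.0)/50) = 2.65

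Simulated mean model SEs are 2.22, 2.34 and 2.64, while the true sampling SD stays at about 2.23. The estimate is unbiased but the interval is too wide.

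Simulated power (60,000 replicates per scenario, t-based intervals standing in for the vague-prior posterior, no baseline covariate). Both rules are shown because 14.5 states both, and they are not equivalent:

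| Scenario | Rule | π = 0 | π = 5 | π = 10 |
|---|---|---|---|---|
| Δ 10, ρ 0.5 | 95% interval above 0 | 78.9% | 77.8% | 74.3% |
| Δ 10, ρ 0.5 | P ≥ 0.95 | 87.2% | 86.6% | 84.3% |
| Δ 5, ρ 0.8 | 95% interval above 0 | 59.1% | 55.2% | 44.1% |
| Δ 5, ρ 0.8 | P ≥ 0.95 | 71.2% | 68.0% | 59.5% |

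With a period term, power under the interval rule stays at about 79% and 59%.

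**Step 5: unequal sequences, ± coding.** Size of bias = π·|n1 − n2|/(n1 + n2), for subjects with both periods.

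- 27/23 (an assumed split): 5·4/50 = 0.4 and 10·4/50 = 0.8 points
- 30/25 (the extremes of the Table 1 range): 5·5/55 = 0.45 and 10·5/55 = 0.91 points

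A period term removes this bias.

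**Step 6: 0/1 codings.** With no true difference, π = −5, ρ = 0.5 and 25/25, the chance that P(β3 > 0) ≥ 0.95 is about 25% with the Test-first indicator (5.4% once period is added) and 39% with the per-period indicator.

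**The case against.** The decision rule uses only the sign of β3. Under ±1, ±½, or components as treatments, β3 is a positive multiple of the difference, so superiority is judged the same way. Hypothesis Testing speaks of the difference between Test and Control, which allows ±½ coding or reporting 2·β3. The predictive probability of success in 14.7 also depends on the sign, so halving leaves it essentially unchanged; only a real period effect would reach it. All of this stands, and it limits the scale problem to an ambiguity in what is reported.

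The period effects are assumed. At 5 points the loss is 1.1 percentage points of power at Δ 10, ρ 0.5 (78.9 − 77.8) and 3.9 at Δ 5, ρ 0.8 (59.1 − 55.2). The 44.1% needs a period effect twice the treatment effect. Blocks of 2 keep allocation near 1:1, the bias stays below one point on a 100-point scale, and with equal sequences the error is conservative. Table 4 rests on a paired test that has no period term either, and section 2.3 calls the study a pilot with exploratory hypotheses. These points fairly limit the severity.

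They do not repair the text. No other section defines Test, the components or BASE. The protection from equal sequences holds only under ± coding or components as treatments; with the Test-first 0/1 indicator β3 is distorted even at 25/25.

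**Conclusion.** The concern holds and should be fixed before analysis. As written, the model omits period and does not establish that β3 is the Test minus Control difference. Depending on coding, a 10-point difference is reported as 5 or 10; under the least coherent coding β3 is a period contrast instead.

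Under ± coding with equal sequences, an ignored period effect costs precision but causes no bias. The power loss under the interval rule, in the two scenarios examined, runs from about 1 to 15 percentage points for assumed effects of 5 to 10 points. Unequal completion adds bias of about 0.4 to 0.9 points. These sizes rest on SD 25, complete pairs, no baseline adjustment and the assumed period effects. The gap in the specification rests on the text alone.

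**What to change.** In 14.5, define component k as period k and write

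μk = μ0 + β1·BASE + β2·sequence + β4·periodk + β3·Tk,

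with Tk = 1 if Test is used in period k and 0 if Control, and the same sign in both periods. β3 is then the Test minus Control difference in VAS points, and in OSDI points through 14.6. Add period to the listed fixed effects, and state whether BASE is the Visit 1 value or each period's own pre-drop value.

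Both changes are needed. Adding period while keeping the sign flip with a per-period 0/1 indicator leaves β3 not estimable. The cost is SAP wording and one coefficient (about one degree of freedom), with no change to data collection.

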#### **The Model:**

Let  $\mathbf{y}_{ijk} = (y_{1ij}, y_{2ij})^T$  denote the comfort scores for the  $i^{\text{th}}$  subject, from  $i^{\text{th}}$  site at 1week follow-up. The likelihood of  $\mathbf{y}_{ij}$  is constructed as follow:

$$\mathbf{y}_{ij} \sim N(\boldsymbol{\mu}, \boldsymbol{\Sigma}),$$

where  $\boldsymbol{\mu} = (\mu_1, \mu_2)^T$  and  $\boldsymbol{\Sigma}$  is a 2x2 variance-covariance matrix. Here  $\mu_i, i = 1, 2$ , are given by:

$$\begin{aligned}\mu_1 &= \mu_0 + \beta_1\text{BASE} + \beta_2\text{sequence} + \beta_3\text{Test}, \\ \mu_2 &= \mu_0 + \beta_1\text{BASE} + \beta_2\text{sequence} - \beta_3\text{Test},\end{aligned}$$

Other baseline characteristics such as age, gender DEQ-5 score will also be included as fixed effects when appropriate.

Non-informative prior distributions will be used for the coefficients in the models as well as for the error terms: Independent vague normal  $N(0,1000)$  priors for the regression

coefficients ( $\mu_0$  and  $\beta$ ) and inverse Wishart  $IW(R,2)$  for  $\Sigma$ .  $R$  is determined by  $S = E[\Sigma] = 4R$  where  $S$  is the sample variance-covariance matrix of the  $y_{ij}$ . The Metropolis sampler algorithm as implemented in the MCMC Procedure (SAS 9.4, SAS Institute, Cary, NC) will be used to estimate the posterior distributions of the unknown parameters. Inferences will be made based on a posterior credible interval for the relevant parameters. Results will be reported as regression coefficient mean estimates with 95% credible intervals.

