## SYNOPSIS

Protocol Title	Clinical Evaluation of two marketed artificial tears in non-contact lens wearing patients
Sponsor	JJV, [name]
Clinical Phase	Post Marketing, Phase 4
Trial Registration	This study will be registered on ClinicalTrials.gov based on the following: the study will be utilizing marketed products to assess endpoints related to comfort.
Test Article(s)	Two artificial tears products: 

• blink® intensive TRIPLE ACTION 3 in 1 eye drops (Test)

• Systane® BALANCE eye drops (Control)

Treatment dosage	Dosage: Instill 1-2 drops OU at least three times a day.
Objectives	The primary objective of this study is to gain clinical insights of the products with respect to ocular comfort after one week of use.
Study Endpoints	Primary endpoint: VAS comfort score Secondary endpoint: OSDI score Other endpoints: DEQ-5, LipiView II®, NITBUT, ocular physiology, subject's reported ocular symptoms, adverse events

Study Design	
The study design is a randomized, double-masked, bilateral, 2 treatment × 2 period, dispensing, 4-visit study:
 
Visit 0: pre-screening with completion of DEQ-5
 
Visit 1: Baseline and eligibility, randomization. Dispense first eye drop solution. LipiView II® measurement at approx.5 mins, 30 mins, 1 hour, and 2 hours post-drops. VAS comfort.
 
Study drops used at least 3x per day for 7-9 days.
 
Visit 2: One-week follow-up - Questionnaires, LipiView II®, NITBUT, slit lamp findings. VAS comfort.
 
Washout period: 7-9 days (habitual artificial tear usage)
 
Visit 3: Baseline, confirm eligibility, dispense second eye drop solution. LipiView II® measurement at approx..5 mins, 30 mins, 1 hour, and 2 hours post drop. VAS comfort.
 
Study drops used at least 3x per day for 7-9 days.
 
Visit 4: One-week follow up, Questionnaires, ®, NITBUT, slit lamp findings, final evaluation. VAS comfort.
 
See the Summary of Visits table at the end of the synopsis for the schematic of the study visits and procedures of main observations.

Sample Size	Approximately 60 non-contact lens wearing subjects are targeted to be enrolled and approximately 50 subjects are targeted to complete the study.
Study Duration	The study will last approximately 3 months and include a 2-month enrollment period.

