### **2.2. Endpoints**

#### **Primary Endpoint:**

The primary endpoint is ocular comfort score at 1-week follow-up using Visual Analogue Scale (VAS) of comfort. VAS of comfort consists of a vertical line which represents continuous scale from 0 (extremely uncomfortable) to 100 (extremely comfortable).

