## 7. STUDY EVALUATIONS

### 7.1. Time and Event Schedule

Table 3: Time and Events

Visit Information	Visit 0 Optional pre-screen	Visit 1 Baseline, dispense drop #1	Visit 2 Follow-up drop #1	Washout	Visit 3 Dispense drop #2	Visit 4 Follow-up drop #2
Time Point			7-9 days after V1	7-9 days	7-9 days after V2	7-9 days after V3
Estimated Visit Duration		3 hours	1.5 hours		3 hours	1.5 hours
Phone/ electronic consent	X					
Study Informed Consent		X				
Inclusion/Exclusion Screening Criteria		X				
Demographics		X				
Medical History & medication review		X	X		X	X
Habitual Artificial Tear usage		X				
DEQ-5	X	X	X		X	X
OSDI		X	X		X	X
Biomicroscopy		X	X		X	X
Eligibility		X				
Randomization		X				
LipiView II®		X	X		X	X
Pre-drop VAS comfort		X			X	
Drop #1 instillation		X				
Drop #2 instillation					X	
LipiView II® follow up (5 minutes, 30 minutes, 60 minutes, 120 minutes)		X			X	
Post-drop VAS comfort/questionnaires (5 minutes, 30 minutes, 60 minutes, 120 minutes)		X			X	
NITBUT		X	X		X	X
Ocular Symptoms		X	X		X	X
Drop Dispensing & Instruction		X			X	
Drop Usage questions		X	X		X	X
Follow-up VAS comfort/questionnaires			X			X
Exit Slit-lamp			X		X	X
Adverse Event Review			X		X	X
Final Evaluation						X

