### 14.4. Level of Statistical Significance

All planned analysis for this study will be conducted with an overall type I error rate of 5%.

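### The baseline term in the primary model is identical in both periods and cancels from the Test-Control contrast, so the Visit 3 pre-drop score adds no precision unless it enters as a within-subject difference

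*Combined protocol and SAP*

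**What the plan says.** Section 14.5 (The Model) writes the first mean as "\mu_0 + \beta_1\text{BASE} + \beta_2\text{sequence} + \beta_3\text{Test". The second mean is the same except that the sign of the Test term is reversed. BASE carries no period index and is not defined anywhere. The text then allows further covariates: "Other baseline characteristics such as age, gender DEQ-5 score will also be included as fixed effects when appropriate". On the covariance it says: "The correlation between measurements across periods will be modeled using unstructured variance-covariance matrix". Section 14.6 applies the same model to OSDI.

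The schedule in section 7.1 (Table 3) marks "Pre-drop VAS comfort" at both Visit 1 and Visit 3, which are steps 1.8 and 3.6 in section 7.2. OSDI is also taken before the drop at both visits (steps 1.7 and 3.5). The synopsis describes Visit 3 as "Baseline, confirm eligibility, dispense second eye drop solution". No text says that the Visit 3 score enters the analysis model.

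**The concern.** In a two-period crossover the treatment effect is estimated from each subject's difference between periods. A covariate with the same value and the same coefficient in both periods is constant within the subject and cannot influence that difference. The baseline adjustment in the printed model therefore looks like a precision measure but does nothing for the primary contrast or for the OSDI contrast.

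A baseline that changes between periods can help, because it may explain part of the within-subject variation. The trial already plans to collect one. What is at stake is some precision for the Test-Control difference, and the risk that two programmers read an undefined BASE differently and get different standard errors.

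**Working it through.** **Inputs.** From section 14.2 and Table 4: 50 completers, true differences (Δ) of 5 and 10, between-period correlation ρ of 0.3, 0.5 or 0.8. Section 14.2 prints 25 as a variance, but Table 4 reproduces only if 25 is the SD. The test is two-sided at 5%, in line with the two-sided 95% interval in 14.5. Not in the documents, so assumed: r, the correlation between the Visit 1 minus Visit 3 baseline difference and the difference between the two follow-up scores.

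**Table 4 first.** The SD of the paired difference is 25 × √(2(1 − ρ)). At ρ = 0.5 this is 25, and the SE is 25/√50 = 3.54. Paired-t power from the noncentral t with n = 50 is 21.6, 28.4 and 59.2% for Δ = 5, and 64.9, 79.2 and 99.2% for Δ = 10. All six printed values reproduce, with no baseline covariate.

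**Cancellation.**
- μ1 = μ0 + β1·BASE + β2·sequence + β3·Test
- μ2 = μ0 + β1·BASE + β2·sequence − β3·Test
- μ1 − μ2 = 2·β3·Test, which contains no BASE
- μ1 + μ2 = 2(μ0 + β1·BASE + β2·sequence)

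The sum cannot bring BASE back. Sequence has its own free coefficient and the covariance is unstructured, so, given the difference, the sum carries no further information on β3. Age, gender and DEQ-5, written at subject level, drop out in the same way.

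**Numerical check.** The bivariate normal model was fitted by maximum likelihood to simulated crossovers (400 trials per setting). The plan calls its priors non-informative, and they are taken as such here.
- 50 complete pairs: the Test-Control estimates with a common BASE and with none agreed to about 1e-13, with the same SE (3.475 and 3.475). This also held with unequal period variances.
- 10 further subjects with period 1 only: cancellation is no longer exact, but the mean SE without and with BASE barely moved (3.409 and 3.415 in one setting, 3.385 and 3.355 in another).

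**What a within-subject baseline term could add.** SE = 3.54 × √(1 − r²), with power on 48 degrees of freedom, at ρ = 0.5:

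| r | √(1 − r²) | SE | Power, Δ = 10 | Power, Δ = 5 |
|---|---|---|---|---|
| 0 | 1.000 | 3.54 | 79.1% | 28.3% |
| 0.2 | 0.980 | 3.46 | 80.7% | 29.3% |
| 0.3 | 0.954 | 3.37 | 82.8% | 30.6% |
| 0.4 | 0.917 | 3.24 | 85.6% | 32.7% |
| 0.5 | 0.866 | 3.06 | 89.3% | 36.0% |

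With equal variances, r = (a − b)/√((1 − ρ)(1 − c)), where a and b are the same-period and cross-period baseline-outcome correlations and c is the correlation of the two baselines. With a = 0.5, b = 0.3 and c = ρ = 0.5, r = 0.2/0.5 = 0.4. If a = b, r = 0 and there is nothing to gain.

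**How the baseline is entered matters.** Empirical SE of the contrast in simulation (compare within rows; the no-baseline column varies by simulation error):

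| r | No baseline | Period-indexed BASE, one shared β1 | Subject mean and deviation, separate coefficients |
|---|---|---|---|
| 0 | 3.60 | 4.01 (+11%) | 3.63 (+1%) |
| 0.2 | 3.53 | 3.67 (+4%) | 3.46 (−2%) |
| 0.4 | 3.54 | 3.24 (−8%) | 3.27 (−8%) |

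A shared β1 forces the between-subject and within-subject slopes to be equal. When the within-subject slope is weak, this adds noise to the difference.

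**The case against.** **BASE may have been meant as period-specific.** The notation in 14.5 is loose with indices in general, and the synopsis calls both visits a baseline. This is plausible, but the equations do not print it. It also would not settle the matter, because a period-indexed BASE with the single printed β1 is the form that can lose precision.

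**The gain is speculative.** This stands. It depends wholly on r, which the documents do not give. For a stable symptom trait with equal same-period and cross-period correlations, r is 0.

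**This is a pilot with exploratory hypotheses, and its sample size was not based on a power calculation.** This also stands, and it limits the weight of the point.

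A reader might go further and infer any of three things that the documents do not support:
- That the primary estimate is biased or the type I error affected. Cancellation of a covariate does neither.
- That Table 4 overstates power. It assumes a paired test with no covariate, which has the precision of the printed model for complete pairs.
- That the Visit 3 baseline is needed to remove drift between the period starts. Section 5.1 randomises the two sequences in blocks of 2, so drift common to all subjects is balanced between treatments. Drift that depends on the first drop would be carry-over, and the Visit 3 baseline would then itself be affected by treatment.

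**Conclusion.** The point holds as a modest precision improvement plus a missing definition. As printed, β1·BASE and the other subject-level covariates do not affect the Test-Control contrast in subjects with both periods, and the effect of single-period subjects is negligible. Nothing in the plan uses the Visit 3 pre-drop VAS or OSDI in the model.

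With n = 50, SD 25, ρ = 0.5 and Δ = 10, a properly entered within-subject baseline term leaves power at about 79% if r = 0, at a cost of about 1% in SE. It raises power to about 81%, 83%, 86% or 89% if r is 0.2, 0.3, 0.4 or 0.5. These are scenarios over an assumed r, not a forecast.

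**What to change.** In 14.5, define baseline as the pre-drop VAS at Visit 1 (step 1.8) and Visit 3 (step 3.6). In 14.6, define it as the OSDI at the same visits (steps 1.7 and 3.5). Replace β1·BASE with two terms that have separate coefficients:
- the subject's mean of the two baselines, common to both periods;
- the period's deviation from that mean, which is equivalent to using the Visit 1 minus Visit 3 difference.

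Do not simply add a period index to BASE while keeping one β1. State that age, gender and DEQ-5, if included at subject level, do not affect the contrast in complete pairs.

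The cost is SAP wording only, since the data are already scheduled. The drawback is that the Visit 3 score follows the first drop and relies on the washout described in 4.2 having worked. Keep the model without the Visit 3 baseline as a prespecified sensitivity analysis.
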